6.2 Screen Failures

If a patient fails to meet an eligibility criterion during the screening period, then the Investigator will complete the screen failure section in the e-CRF.

Patients who have signed informed consent, but do not complete screening and who do not receive treatment on study with SNS-301 may be replaced for efficacy, toxicity and translational analyses.

6.3 Strategies for Recruitment and Retention

It is anticipated that up to 15 sites will participate in the study in the United States. Patients will be recruited from either standalone outpatient clinics or hospital clinics.

7. STUDY INTERVENTION

7.1 Study Intervention(s) Administration

7.1.1 *Study Treatment Description*

7.1.1.1 *SNS-301 Treatment*

The HAAH Nanoparticle Vaccine drug substance is a recombinant bacteriophage lambda construct that is engineered to display a fusion protein of phage gpD and a portion of the HAAH protein sequence. The HAAH-1 λ (SNS-301) construct contains 199 amino acids from the N-terminal region (amino acids 113 – 311) of the molecule.

The drug substance is characterized by testing that includes appearance, pH, and identity by dot blot using HAAH-specific monoclonal antibody, impurities (bioburden, endotoxin, host cell protein), determination of size distribution by particle analysis, quantitation by particle analysis, protein determination and potency by antigen enzyme-linked immunosorbent assay (ELISA). The drug product is a sterile, preservative-free solution.

7.1.1.2 *Pembrolizumab Treatment*

Keytruda® (Pembrolizumab) is an FDA-approved programmed death receptor-1 (PD-1)-blocking antibody that is indicated for the treatment of patients with recurrent or metastatic squamous cell carcinoma of the head and neck (HNSCC). humanized monoclonal antibody that blocks the interaction between PD-1 and its ligands, PD-L1 and PD-L2. Pembrolizumab is an IgG4 kappa immunoglobulin with an approximate molecular weight of 149 kDa. Pembrolizumab is produced in recombinant Chinese hamster ovary (CHO) cells.

KEYTRUDA may be supplied in two different formulations:

- KEYTRUDA for injection is a sterile, preservative-free, white to off-white lyophilized powder in single-dose vials. Each vial is reconstituted and diluted for intravenous infusion. Each 2 mL of reconstituted solution contains 50 mg of pembrolizumab and is formulated in L-histidine (3.1 mg), polysorbate 80 (0.4 mg), and sucrose (140 mg). May contain hydrochloric acid/sodium hydroxide to adjust pH to 5.5. Or
- KEYTRUDA injection is a sterile, preservative-free, clear to slightly opalescent, colorless to slightly yellow solution that requires dilution for intravenous infusion. Each vial contains 100 mg of pembrolizumab in 4 mL of solution. Each 1 mL of solution contains 25 mg of pembrolizumab and is formulated in: L-histidine (1.55 mg), polysorbate 80 (0.2 mg), sucrose (70 mg), and Water for Injection, USP.

For the purpose of this protocol, study treatment is defined as SNS-301 and pembrolizumab.

7.1.2 *Dosing, Administration and Preparation*

The study treatment will be administered only to patients included in this study following the procedures set out in this clinical study protocol. Administration of the study treatment will be supervised by the Investigator or sub-Investigator. Details of the exact time of administration of medication (day/month/year, hour:minute) will also be documented in the eCRF.

7.1.2.1 *SNS-301 Dosing*

The vaccine will be delivered intra-dermally by a single-use 3M® hollow microstructured transdermal system (hMTS) device. Patients will be administered intradermally the SNS-301 dose of 1.0×10^{11} particles in 1 mL per administration.

Patients will receive SNS-301 on a staged schedule starting every three weeks for four doses, every six weeks for 6 doses and thereafter every twelve weeks.

When pembrolizumab and SNS-301 are dosed on the same day, SNS-301 will be dosed approximately 1 hour after IV infusion of pembrolizumab for the first dose. Subsequent doses of SNS-301 and pembrolizumab can be dosed in any order.

A 60 minutes observation period is recommended for the first dose on this study and 30 minutes for subsequent doses.

Additional information on Dosing, Administration and Preparation can be found in the pharmacy manual for SNS-301.

7.1.2.2 *Pembrolizumab Dosing*

A fixed dose of 200 mg pembrolizumab as an intravenous infusion over 30 minutes every 3 weeks or a fixed dose of 400 mg pembrolizumab, as an intravenous infusion over 30 minutes every 6 weeks will be administered.

A sterile, non-pyrogenic, low-protein binding 0.2 micron to micron in-line or add-on filter will be utilized. Do not co-administer other drugs through the same infusion line.

A 60 minutes observation period is recommended for the first dose on this study and 30 minutes for subsequent doses.

Additional information of Dosing, Administration and Preparation can be found in the package insert for Keytruda https://www.merck.com/product/usa/pi_circulars/k/keytruda/keytruda_pi.pdf

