^u Pembrolizumab will be given every 3 weeks until confirmed disease progression, unacceptable toxicity, deemed intolerable by investigator or up to 24 months in patients without disease progression. The window for each visit is ± 3 days unless otherwise noted. A 60 minutes observation period is recommended for the first dose and 30 minutes for subsequent doses.

^v SNS-301 is administered every 3 weeks until week 9 (i.e., 4 doses). Then every 6 weeks for 6 more doses (until week 45). Thereafter it will be administered every 12 weeks until confirmed disease progression, unacceptable toxicity, deemed intolerable by investigator or up to 24 months in patients without disease progression. The window for each visit is ± 3 days unless otherwise noted. A 30-minute observation period is recommended after each study treatment.

^w Survival follow-up information will be collected via telephone calls, patient medical records, and/or clinical visits approximately every 3 months for up to 3 years, until death, lost to follow-up, withdrawal of consent, or trial termination by Sponsor. All patients will be followed for survival and new anticancer therapy information unless the patient requests to be withdrawn from follow-up; this request must be documented in the source documents and signed by the investigator. If the patient discontinues study treatment without documented clinical disease progression, every effort should be made to follow up regarding survival, progression (, and new anti-cancer therapy.

Pembrolizumab Schedule – Every 6 weeks

	Screening ^a	Cycle 1 Day 0	Cycle 2 Week 3	Cycle 3 Week 6	Cycle 4 Week 9	Every 6 weeks	Every 12 weeks	Discontinuation Visit ^b	Follow-up
	Day -28 to Day -1								
Signed Informed Consent Form(s)	X								
Medical, surgical, and cancer histories, including demographic information^c	X								
Inclusion/Exclusion criteria	X	X							
Complete Physical exam^d	X								
Targeted Physical exam^e		X ^f	X ^f	X ^f	X ^f	X ^f		X	
ECOG performance status^f	X	X	X	X	X	X		X	
HIV, Hep B and Hep C serology^g	X								
Concomitant Medications^h	X	X	X	X	X	X		X	
Anticoagulant specific drug and/or anticoagulant factor Xa levelsⁱ	X	X	X	X	X	After week 12, Q6w until week 42, thereafter Q12w			X
For patients on anticoagulants only									
Vital Signs and Weight^j	X	X	X	X	X	X		X	
Height	X								
12-lead ECG^k	X								
Tumor Imaging^l	X	Q6w from Day 0 until ~12 months, there after Q12w							

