^t AEs will be collected from the time of informed consent until 30 days after the last dose of study treatment or until initiation of another anti-cancer therapy, whichever occurs first. SAEs and AESIs will be collected from the time of informed consent until 90 days after the last dose of study treatment or until initiation of anti-cancer therapy, whichever occurs first.

^u Pembrolizumab will be given every 6 weeks until confirmed disease progression, unacceptable toxicity, deemed intolerable by investigator or up to 24 months in patients without disease progression. **After week 9, the pembrolizumab and SNS-301 visits will not coincide. The SNS-301 dosing should not be adjusted. The investigator may choose to give a 3-week dose (i.e., pembrolizumab 200 mg) in order for the visits to align. The investigator should consult the sponsor if there are questions regarding aligning the study treatment schedule.** The window for each visit is \pm 3 days unless otherwise noted. A 60 minute observation period is recommended for the first dose and 30 minutes for subsequent doses.

^v SNS-301 is administered Day 0, Week 3, Week 6 and Week 9, then every 6 weeks for 6 more doses (until week 48). Thereafter it will be administered every 12 weeks until confirmed disease progression, unacceptable toxicity, deemed intolerable by investigator or up to 24 months in patients without disease progression. The window for each visit is \pm 3 days unless otherwise noted. A 30-minute observation period is recommended after each study treatment.

^w Survival follow-up information will be collected via telephone calls, patient medical records, and/or clinical visits approximately every 3 months for up to 3 years, until death, lost to follow-up, withdrawal of consent, or trial termination by Sponsor. All patients will be followed for survival and new anticancer therapy information unless the patient requests to be withdrawn from follow-up; this request must be documented in the source documents and signed by the investigator. If the patient discontinues study treatment without documented clinical disease progression, every effort should be made to follow up regarding survival, progression and new anti-cancer therapy.

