7.1.2.3 Study Treatment Administration

Patients will receive their study treatment as described in Section 7.1.2.1 & 7.1.2.2 until disease progression, unacceptable toxicity, deemed intolerable by investigator or up to 24 months in patients without disease progression.

A safety run-in will be performed using a modified rolling six design which will enroll up to six patients (safety analysis patients) as per Section 5.2. Once the safety run-in has been cleared and communicated with Investigator's further enrollment may occur.

There will be no dose reductions. See Section 7.5 for Dose Modifications.

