9. STUDY ASSESSMENTS AND PROCEDURES

Refer to the Time and Events Schedule [Table1](#) for an outline of the procedures required at each visit along with their associated windows. All patients must sign and date the most current approved ICF before any study specific procedures are performed. Procedures conducted as per standard of care or routine clinical management that are obtained before signing of the ICF may be utilized for screening/baseline purposes. All screening assessments may be performed within 28 days of Day 0 with the exception of screening labs (hematology and chemistry) which may be performed within 10 days of Day 0. Patients who discontinue will be asked to return to the clinic within 30 days of the last dose for a discontinuation visit. Generally, protocol waivers or exemptions will not be granted without discussion with the Sponsor.

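### The dosing section recommends 60 minutes of observation for the first SNS-301 dose, but the SNS-301 footnote in both Table 1 schedules recommends 30 minutes with no first-dose exception (minor)

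*Protocol*

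**What the plan says.** The protocol gives an observation period after SNS-301 in two places.

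- **Section 7.1.2.1, SNS-301 Dosing:** "A 60 minutes observation period is recommended for the first dose on this study and 30 minutes for subsequent doses". Section 7.1.2.2 has the identical sentence for pembrolizumab. SAP 2.3 carries the 60/30 recommendation separately under each drug.
- **Table 1, footnote v (SNS-301), three-weekly and six-weekly pembrolizumab schedules:** "A 30-minute observation period is recommended after each study treatment". SAP Appendix A, which reproduces the three-weekly schedule, repeats it.

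The neighbouring footnote u, for pembrolizumab, does separate the first dose from later ones: "A 60 minutes observation period is recommended for the first dose and 30 minutes for subsequent doses" in the three-weekly schedule, with the same content in the six-weekly one.

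Three other statements bear on how these are read. Section 7.1.1.2 says "For the purpose of this protocol, study treatment is defined as SNS-301 and pembrolizumab". Section 7.1.2.1 fixes the order on Day 0: "SNS-301 will be dosed approximately 1 hour after IV infusion of pembrolizumab for the first dose". Section 9 sends sites to Table 1 "for an outline of the procedures required at each visit along with their associated windows".

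**The concern.** For the first SNS-301 injection, the dosing section and the visit schedule recommend different observation periods. The schedule is the page a clinic is likely to have open on the day, and its SNS-301 footnote gives the shorter period. Nothing in it tells the reader that a longer one is recommended elsewhere.

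What is at stake is bedside observation between 30 and 60 minutes after the first SNS-301 dose. The protocol is otherwise careful about first exposure. Section 7.4.3 notes that SNS-301 had not been added to pembrolizumab before this trial. Section 5.2 imposes a one-week wait between the first and second patients. Section 9.3.10 makes systemic administration site reactions an event of special interest. A shorter first-dose observation that arises only from a footnote's wording would not fit that approach.

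**Working it through.** No sample size, power or error rate is involved. The check is a comparison of texts, plus the Day 0 timing.

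**1. The two SNS-301 instructions side by side**

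| SNS-301 dose | Protocol 7.1.2.1 and SAP 2.3 | Footnote v, both Table 1 schedules and SAP Appendix A |
|---|---|---|
| First | 60 minutes | 30 minutes |
| Later | 30 minutes | 30 minutes |

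The texts differ only at the first dose: 60 − 30 = 30 minutes, a ratio of 30/60 = 0.5. All of them are current text, not amendment-log entries.

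**2. Does the pembrolizumab observation hour in footnote u cover the gap?**

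Inputs: a 30-minute infusion (7.1.2.2), SNS-301 about 1 hour after the infusion (7.1.2.1), 60 minutes of pembrolizumab observation (footnote u), and 30 minutes after SNS-301 (footnote v). I assume that pembrolizumab observation runs from the end of the infusion, which leaves the most time. The schedule alone then gives

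minutes observed after SNS-301 = max(30, pembrolizumab observation still to run).

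- SNS-301 given 1 hour after the infusion **ends**: 60 − 60 = 0 minutes still to run, so max(30, 0) = 30.
- SNS-301 given 1 hour after the infusion **starts**, which is 60 − 30 = 30 minutes after it ends: 60 − 30 = 30 minutes still to run, so max(30, 30) = 30.

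Counting pembrolizumab observation from the start of the infusion leaves less time to run, so the result is still 30. Under each of these readings the schedule gives 30 minutes against 60 in 7.1.2.1. Footnote u does not close the gap.

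**3. Does the wording of footnote v close it?**

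Study treatment means both drugs, so footnote v can be read as a general 30-minute minimum. Observing for 60 minutes meets that minimum and 7.1.2.1 together, so the two texts can both be followed. But the footnote does not state the longer first-dose period, so a reader of the schedule would not know of it.

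**4. Does either text take precedence?**

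Section 7.1.2.3 points to the dosing sections for giving treatment: "Patients will receive their study treatment as described in Section 7.1.2.1 & 7.1.2.2 until disease progression". Section 9 calls the schedule an outline. Both favour 7.1.2.1 as the controlling text, but no rule of precedence is stated.

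**The case against.** The strongest reply is that this is an editorial mismatch. Both periods are recommended, neither is required, and 60 minutes satisfies both. Sites are directed to 7.1.2.1 and 7.1.2.2 for administering treatment, and no document shows a site working from the footnote alone. All of that stands, and it limits the weight of the point.

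A second reply is that the 60 minutes in 7.1.2.1 may not be meant for SNS-301. The sentence speaks of the first dose on the study, follows the rule that separates the two first doses by about an hour, and matches the pembrolizumab sentence word for word. It could describe the hour between the two drugs, or have been carried over. Footnotes u and v would then be coherent: 60 minutes after pembrolizumab, then 30 after SNS-301. This reading is open but less natural, because the sentence sits under the SNS-301 heading, 7.1.2.2 states the pembrolizumab recommendation separately, and SAP 2.3 keeps the same separation. The pharmacy manual that 7.1.2.1 cites might settle the matter, but it is not among the documents.

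A reader might also infer that first-dose safety monitoring is compromised. The documents do not support that. Both periods are compatible with the administration-site assessment in 9.3.10, set at 30 minutes or more after dosing. Collection of events of special interest to 90 days after the last dose (9.2.14.5) is unaffected. Nothing in the documents shows reactions clustering 30 to 60 minutes after SNS-301, and no dose-limiting toxicities had been reported at the 29 October 2020 cutoff (3.1.2).

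**Conclusion.** The inconsistency is real and minor. A site that follows footnote v and not 7.1.2.1 would observe for 30 minutes instead of 60 after the first SNS-301 dose, once per patient. The number of patients affected is unknown, because the documents do not show how many sites work from the schedule. Planned enrolment does not measure it.

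The conclusion rests on reading the 7.1.2.1 sentence as applying to SNS-301, as its heading indicates. Two stronger statements would go too far. A site that observes for 30 minutes is not in deviation, since both periods are recommendations. Nor do the documents establish that 60 minutes was the intended figure; they show only that the sponsor's texts disagree. No endpoint, analysis population, sample size or error rate is touched.

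**What to change.** The sponsor should confirm the intended first-dose period. Sixty minutes is the sensible default, because it is the more protective figure and agrees with the dosing section. On that basis, replace the last sentence of footnote v in both Table 1 schedules with: *A 60-minute observation period is recommended after the first SNS-301 dose and 30 minutes after subsequent doses.* Make the same change to footnote v in SAP Appendix A. Naming SNS-301 in place of study treatment also stops the footnote from appearing to set 30 minutes for the first pembrolizumab infusion, where footnote u says 60.

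If the sponsor confirms 30 minutes, leave the footnotes and correct the SNS-301 sentence in both Protocol 7.1.2.1 and SAP 2.3; changing the protocol alone would leave the SAP inconsistent.

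The default fix costs one sentence in each of two protocol footnotes and one SAP footnote, which can go into the next amendment. At sites that were following the footnote, it adds up to 30 clinic minutes, once per patient.

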7.1.2.3 Study Treatment Administration

Patients will receive their study treatment as described in Section 7.1.2.1 & 7.1.2.2 until disease progression, unacceptable toxicity, deemed intolerable by investigator or up to 24 months in patients without disease progression.

A safety run-in will be performed using a modified rolling six design which will enroll up to six patients (safety analysis patients) as per Section 5.2. Once the safety run-in has been cleared and communicated with Investigator's further enrollment may occur.

There will be no dose reductions. See Section 7.5 for Dose Modifications.

7.2 Preparation/Handling/Storage/Accountability

7.2.1 Acquisition and Accountability

SNS-301, including the 3M® hMTS transdermal system, will be packaged by the Sponsor, and supplied in an open-label basis. The Investigator or designee is responsible for storing, administering and accounting for the SNS-301 according to the instructions provided by the Sponsor. SNS-301 shall be dispensed in accordance with the Investigator's prescription and it is the Investigator's responsibility to ensure that an accurate record of SNS-301 received, issued, returned and destruction is maintained.

SNS-301, including the 3M® hMTS transdermal system should be placed in a proper disposal container following administration . The person responsible for drug dispensing is required to maintain adequate records of SNS-301. These records (e.g., product accountability log) include the date the SNS-301 is received from the Sponsor and administered to the patient.

After review by the Sponsor or designee, all used and unused SNS-301 should be discarded at the investigational site, in accordance with the site's institutional SOPs and/or policies, and a destruction certificate obtained. The Investigator or designee will submit the copy of Product Accountability Log to the Sponsor. If the investigational site is unable to destroy SNS-301, the Sponsor will provide alternate instructions for destruction.

Under no circumstances will the Investigator supply SNS-301 to a third party, allow SNS-301 be used other than as directed by this Clinical Trial Protocol, or dispose of SNS-301 in any other manner.

Any quality issue noticed with the receipt or use of a SNS-301, including 3M® hMTS transdermal system (deficiency in condition, appearance, pertaining documentation, labeling, expiry date, etc.) should be promptly notified to the Sponsor, who will initiate a complaint procedure.

A potential defect in the quality of the SNS-301 may be subject to a recall procedure by the Sponsor. In this case, the Investigator will be responsible for promptly addressing any request made by the Sponsor, to recall SNS-301 and eliminate potential hazards.

7.2.2 Formulation, Appearance, Packaging and Labeling for SNS-301 and Pembrolizumab

The supplies will be labeled with a minimum of the following:

- Sponsor's name and address
- Content of the cartridge
- Lot/Batch Number
- "Caution: New Drug--Limited by Federal (or United States) law to investigational use."

Drug supply will be labeled in accordance to local regulations if study is run outside of the United States.

The 3M® hollow microstructured transdermal system (hMTS) device will be labeled with the following:

- Lot number
- Hazard classification
- Date of manufacture
- Storage conditions
- "For human clinical evaluation use" and "Caution - Investigational device. Limited by Federal (or United States) law to investigational use."
- Sponsor's name and address

Refer to the SNS-301 Study Pharmacy Manual for a description of the process of preparation for study drug administration

Pembrolizumab will be labeled as per the manufacture's specification.

7.2.3 Product Storage and Stability

The SNS-301 is stored at 2 – 8 °C. Temperature excursions to $\leq 25^{\circ}\text{C}$ for less than 24 hours are acceptable. Storage at $\leq 25^{\circ}\text{C}$ for less than 24 hours is cumulative. Time spent at this temperature should be recorded in the drug accountability records.

The 3M® hollow microstructured transdermal system (hMTS) device can be maintained at room temperature.

Pembrolizumab will be maintained as per the manufacture's specification.

7.3 Randomization and Blinding

This is an open-label, single-arm study; there will be no randomization or blinding.

All patients who sign the informed consent form (ICF) will be assigned a patient study number which will be retained for the duration of the study.

7.4 Concomitant Therapy

All treatments including any prescription or over the counter medications taken by the patients seven days prior to screening and at any time during the study are regarded as concomitant treatments and must be documented in the appropriate section of the e-CRF. At subsequent visits, changes to current medications or medications used since the last documentation of medications will be recorded. Concomitant medications will be collected until 30 days after the last dose of study medication or until the start of a new anti-cancer treatment, whichever comes first.

7.4.1 *Allowed concomitant treatments*

The following concomitant treatments are permitted during this study:

- Supportive treatment will be given as medically indicated.
- Prophylactic antiemetic premedication including corticosteroids (low dose \leq 10 mg/day prednisone equivalent) and 5-hydroxytryptamine 3 antagonists.
- Supportive treatment with cannabis will be allowed, if medically indicated.

7.4.2 *Prohibited Medications or Treatments During Study*

Medications such as those listed below are not permitted in the course of the trial:

- Concurrent treatment with other investigational drugs
- Concurrent treatment with any other anticancer therapy including radiotherapy
- Traditional herbal medicines should not be administered because the ingredients of many herbal medicines are not fully studied, and their use may result in unanticipated drug-drug interactions that may cause or confound assessment of toxicity. However, if the investigator feels herbal medication is warranted the Sponsor should be consulted
- Initiation or increased dose of granulocyte colony-stimulating factors (e.g., granulocyte colony-stimulating factor, granulocyte/macrophage colony-stimulating factor, and/or pegfilgrastim) is strongly discouraged
- Patients are not allowed to receive immunostimulatory agents, including but not limited to IFN- α , IFN- γ , or IL-2, during the entire trial. These agents, in combination with study treatment, could potentially increase the risk for autoimmune conditions

7.4.3 *Rescue Medication*

This is the first time the SNS-301 is given in addition to pembrolizumab to any patients. Although most immune-mediated adverse events observed with immunomodulatory agents have been mild and self-limiting, such events should be recognized early and treated promptly to avoid potential major complications. Discontinuation of SNS-301 or pembrolizumab may not have an immediate therapeutic effect due to the long half-life of the drug or longer drug effect, and there is no available antidote for the study treatment. In severe cases, immune-mediated toxicities may be acutely managed with topical corticosteroids, systemic corticosteroids, mycophenolate, or TNF- α inhibitors per investigator's discretion.

For instruction on how to handle pembrolizumab immune response adverse events refer to the pembrolizumab package insert.

Patients should receive appropriate medical intervention necessary to treat medical conditions as they arise.

7.5 *Dose Modification and/or Interruption*

For pembrolizumab, follow the package insert for dose modification instructions.

For SNS-301, there will be no dose reductions allowed for this study.

In case of non-DLT AE (grade 2 NCI-CTCAE V5.0 drug related AE), the dosing interval can be extended to up 42 days to allow the recovery from a related toxicity and the patient will resume at the same dose. If the patient experiences the same grade or higher toxicity and same grade requiring a dose-delay at the subsequent cycle, the patient should be discontinued from study treatment.

Should there be a clinically significant AE or SAE recorded relating to a patient receiving anticoagulants, such as clinically noted bleeding, administration of SNS-301 will be held until the AE/SAE returns to baseline. Should there be two individual events of SNS-301 interruption for the same patient, then SNS-301 will be discontinued after consultation with the Medical Monitor and Study Sponsor.

If a patient is unable to receive study treatment (e.g., due to COVID19) the dosing interval can be extended up to 42 days after consultation with the Sponsor and the rationale to be documented.

Treatment with SNS-301 may continue if pembrolizumab is discontinued by the Investigator, if prior to 24 months. If both study treatments are stopped for >42 days then the patient should be discontinued from study treatment and continue to the study follow up phase.

